6.3 PATIENT SETS ANALYSED

The following analysis sets will be defined for this trial:

Enrolled set (ES)

This patient set includes all patients who signed informed consent. It will be used for display of patient disposition.

Randomized set (RS)

This patient set includes all patients who were randomized in the trial. Treatment assignment will be as randomised. It will be used for display of disposition, IPD and etc.

Safety analysis set (SAF)

This patient set includes all patients who were randomised and received at least one dose of study drug. It will be the main analysis set for presentation of safety data. Patients will be analyzed according to the actual treatment.

Safety analysis set – Post Week 16 (SAF-post 16)

This patient set includes all patients in SAF who received at least one dose of study drug after, and including, Week 16. It will be the main analysis set for presentation of safety data after Week 16 only. Patients will be analyzed according to the actual treatment after week 16.

Full Analysis Set (FAS)

This patient set includes all patients who were randomised, received at least one dose of study drug and had a baseline for the primary endpoint. Treatment assignment will be as randomised. This is the main analysis set for presentation of efficacy data.

Full Analysis Set – Post Week 16 (FAS-post 16)

[figure not shown]
This patient set includes all patients in the FAS and had received at least one dose of study drug after, and including Week 16. Treatment assignment will be as randomised. This is the set for additional analysis of efficacy data post Week 16.

Per-Protocol Set (PPS)

This patient set includes all patients in the FAS set who adhered to the CTP without any iPDs which are flagged for exclusion from the PPS in the table above. The PPS will be used for sensitivity analysis on the primary efficacy endpoint.

Modified FAS set (m-FAS)

This patient set includes all patients in the FAS set excluding pre-identified questionable cases (mild cases) based on mQC (medical quality control) review where the severity of PPP could not be clarified and confirmed based on the descriptive review and quality control of the photo documentation. The m-FAS will be used for sensitivity analysis on the primary efficacy endpoint and selected secondary endpoints.

Handling of Treatment Misallocations in Analysis Sets

If a patient is randomized but not treated, they will not be included into efficacy or safety analysis according to FAS (including FAS-post 16), m-FAS, PPS and SAF (including SAF-post 16).

If a patient is treated but not randomized, they will be excluded from both efficacy analysis and safety analysis by definition. However, patients under such circumstances will be described separately in the final clinical trial report.

If a patient is randomized but took incorrect treatment during the study, then:

- For efficacy analyses according to FAS (including FAS-post 16), m-FAS and PPS, they will be reported under their randomized treatment groups.
- For safety analyses using the SAF,
 - For Arm1-4: If a patient is planned to receive multiple dose administrations of Spesolimab, then patients will be reported under their randomized treatment group for safety analysis because the overall safety profile is expected to be driven by the amount of Spesolimab received in totality over the entire treatment duration. It is not expected that the safety profile will deviate from the planned treatment regimen if the subject receives only a few vials of the incorrect medication at only some dosing occasions.
 - For Arm 5: If a patient is planned to receive multiple dose administrations of placebo (prior to Week 16 only), then patients will be reported under their randomized treatment group for safety analysis if the patient receives no dose of randomized Spesolimab during this treatment period (i.e., prior to Week 16). If the patient receives ≥ 1 syringe of randomized Spesolimab during this treatment period, then the patient will be assigned to Arm 4 (lowest dose of Spesolimab planned in the trial before week 16).
- For safety analyses using the SAF-post 16,
 - For Arm1-5: If a patient is planned to receive multiple dose administrations of Spesolimab, then patients will be reported under their randomized treatment group for safety analysis because the overall safety profile is expected to be driven by the amount of Spesolimab received in totality over the entire treatment duration. It is not expected that the safety profile will deviate from the planned treatment regimen if the subject receives only a few vials of the incorrect medication at only some dosing occasions.

[Table 6.3: 1](#) illustrates the data sets which are to be used for each category class of endpoints, and the approaches used with regard to missing data. For explanation of the different methods of handling missing data, cf. [Section 6.6](#).

Table 6.3: 1 Patient sets analysed

Class of endpoint	Patient set					
	ES	RS	SAF (including SAF-post 16)	FAS (including FAS-post 16, m-FAS)	PPS	█
Disposition	OR	OR				
Compliance and exposure			OR			
iPD		OR				
Demographic/baseline characteristics			OR	OR		
CM			OR			
Primary efficacy endpoint				EC-MMRM, EC-MMRM ¹ EC-EP-MMRM ¹ EC-E19-MMRM ¹ EC-ID-MMRM ¹ EC-MI ¹ , OC ² , OC-IR ²	EC-MMRM ¹	
Secondary efficacy endpoints (Binary)				EC-NRI, EC-NRI ^{1,3} EC-EP-NRI ^{1,3} EC-E19-NRI ^{1,3} EC-ID-NRI ^{1,3} EC-BRI ^{1,3} OC ² , OC-IR ²		
Secondary efficacy endpoints (Continuous)				EC-MMRM, EC-MMRM ^{1,3} OC ² , OC-IR ²		
	█	ADA/Nab				OR

¹ sensitivity analysis or subgroup analysis
² descriptive display only
³ selected endpoints.

EC: Primary estimand for binary and continuous efficacy endpoints. Any data collected after use of any rescue therapy or after 6 weeks following last drug administration if patient early discontinued treatment (to allow for incorporation of the continuing maximum treatment effect period) are censored.

[figure not shown]
EC-EP: Alternative estimand for binary and continuous efficacy endpoints. Any data collected after use of any rescue therapy or restricted therapy for other purpose or after 6 weeks following last drug administration if patient early discontinued treatment (to allow for incorporation of the continuing maximum treatment effect period) are censored.

[figure not shown]
EC-E19: Alternative estimand for binary and continuous efficacy endpoints. Any data collected after use of any rescue therapy or after the first visit with missing treatment due to COVID-19 or after 6 weeks following last treatment before or at discontinuation (to allow for incorporation of the continuing maximum treatment effect period) are censored.

EC-ID: Alternative estimand for binary and continuous efficacy endpoints. Any data collected after use of any rescue therapy are censored.

"NRI", "MMRM" and "MI" represent analyses involving imputed data, cf. [Section 6.6.2](#).

OC = observed cases excluding values after any use of rescue medication or 6 weeks following last drug administration if patient early discontinued treatment, OC-IR = observed cases including also values after any rescue medication or treatment discontinuation, OR = original results.

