7.2 PLANNED ANALYSES

7.2.1 General considerations

There will be 3 main patient populations in this trial for analyses: the full analysis set (FAS), the safety analysis set (SAF), and the per-protocol set (PPS).

Safety Analysis Set (SAF)

This patient set includes all patients who were randomised and received at least one dose of study drug. It will be the main analysis set for presentation of safety. Patients will be analyzed according to the actual treatment.

Full Analysis Set (FAS)

This patient set includes all patients in the SAF who had a baseline for the primary efficacy endpoint. Treatment assignment will be as randomised. This is the main analysis set for presentation of efficacy data.

Per-Protocol Set (PPS)

This patient set includes all patients in the FAS who adhered to the CTP without any IPDs (potentially affecting the study outcome) which lead to exclusion from the PPS. This set will be used for sensitivity analysis on the primary efficacy endpoint. Important deviations of the protocol will include violations of the key inclusion and exclusion criteria, incorrect medications taken, concomitant use of restricted medications, and any other deviations of the protocol deemed important by the study team. All decisions concerning important protocol deviations will be made prior to un-blinding of the database for the primary endpoint analysis at week 16, and a full list of such deviations will be provided in the trial Integrated Quality and Risk Management Plan (IQRMP).

Further analysis sets, [REDACTED], will be defined in the Trial Statistical Analysis Plan (TSAP).

Standard statistical parameters (number of non-missing values, mean, standard deviation (SD), median, quartiles, minimum and maximum) or frequency tables (including patient frequencies and percentages) will be calculated where appropriate.

The following analyses of this trial protocol, in chronological order, are planned:

Week 16 Primary Analysis

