
For AE, the additional safety tables for loading dose stage will be produced by re-grouping patients based on their loading doses [REDACTED] using SAF. The outputs

will include on-treatment data up to the first maintenance dose at week 8. If patient early discontinued from treatment prior to week 8 or missed treatment at week 8, then the safety data up to Day 71 (the right limit of the extended time window of week 8) will be included:

- Overview on TEAE
- TEAE by SOC, preferred term
- Serious TEAE
- All AESI
- UDAEC

AE over on-treatment period

In the final analysis, the additional selected tables for the overall period will be produced based on SAF to report AE occurring during whole treatment period from Day 1. Note that only Arm 1-4 will be reported:

- Overview on TEAE
- TEAE by SOC, preferred term
- Serious TEAE
- All AESI
- UDAEC

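### The SAP's rule for misdosed patients conflicts with the actual-treatment definition of the safety sets, and its move of Arm 5 patients to Arm 4 has no end date in safety displays that span Week 16

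*SAP*

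**What the plan says.** **Definitions.** Protocol 7.2.1 says of the SAF: "Patients will be analyzed according to the actual treatment". SAP 6.3 repeats this: "It will be the main analysis set for presentation of safety data. Patients will be analyzed according to the actual treatment". For SAF-post 16 it says: "Patients will be analyzed according to the actual treatment after week 16". None of the three carries a qualifier or refers to another rule.

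**Misallocation rule** (SAP 6.3, *Handling of Treatment Misallocations in Analysis Sets*). For randomised patients who took incorrect treatment:

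- SAF, Arms 1-4: the instruction is "then patients will be reported under their randomized treatment group for safety analysis because the overall safety profile is expected to be driven by". The driver it then names is total spesolimab exposure. The SAP adds that the profile should not depart from plan "if the subject receives only a few vials of the incorrect medication at only some dosing occasions".
- SAF, Arm 5: the trigger for a move is worded "If the patient receives ≥ 1 syringe of randomized Spesolimab during this treatment period". The consequence, with the reason for choosing that arm in brackets, is worded "then the patient will be assigned to Arm 4 (lowest dose of Spesolimab planned in the trial before week 16".
- SAF-post 16, Arms 1-5: as randomised, with the same reasoning as for Arms 1-4.

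**Displays.** SAP 7.8 bases the separate post-Week-16 AE and laboratory-abnormality tables on SAF-post 16. It bases the whole-period AE tables on the SAF from Day 1, with the remark "Note that only Arm 1-4 will be reported". SAP 7.8.2 and 7.8.3 base the final laboratory and vital-sign last, minimum and maximum values on the SAF. These run over the whole treatment period for Arms 1-4 and are split at Week 16 only for Arm 5.

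**The concern.** There are two separate problems.

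First, actual and randomised treatment differ only for misdosed patients. For those patients in Arms 1-4 (and in Arms 1-5 of SAF-post 16) the rule returns the randomised arm, so the actual-treatment definition never takes effect. SAP Section 4 says the protocol's analyses run as planned apart from the adaptations it lists, and this departure is not among them.

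Second, the Arm 4 label for a drug-exposed placebo patient is justified by doses before Week 16 but is not confined to that period. After Week 16, Arm 5 goes onto the maintenance regimen shared with Arms 1 and 3. Protocol 7.2.3 treats that regimen as distinct from Arm 4's: its comparison of the two is q4w against q8w.

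Protocol 2.1.1 says the target dose will be estimated while accounting for safety, and Arms 2-4 are planned at only 20 patients each. A misplaced patient therefore blurs the dose-safety comparison, most visibly in the lowest-dose column.

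**Working it through.** The plan gives no figure for this point, so the check compares the texts and adds simple arithmetic for scale.

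**1. Definition against rule**

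| Set and arms | Definition | Rule for misdosed patients | Agree? |
|---|---|---|---|
| SAF, Arms 1-4 | actual treatment | as randomised, no limit | No |
| SAF, Arm 5 | actual treatment | Arm 4 after one or more active syringes before Week 16 | Partly: moves out of placebo |
| SAF-post 16, Arms 1-5 | actual treatment after Week 16 | as randomised, no limit | No |

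**2. How uneven the rule is.** The flow chart has dosing on Day 1 and at Weeks 1, 2, 3, 4, 8 and 12 before Week 16, which is 7 visits. At 4 syringes per dosing visit that gives 7 × 4 = 28 syringes. An Arm 5 patient moves after 1/28 = 3.6% of syringes. If four syringes are given only at the four 4-weekly visits (an assumption), the figure is 1/16 = 6.3%. An Arm 1-4 patient with wrong medication at every visit (28/28) does not move.

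**3. How far apart the arms are.** The doses are redacted, but the linear contrasts in SAP Table 7.4: 2 are weighted by arm size. Dividing by 40/20/20/20/40 and taking the distance from placebo recovers the relative planned totals before Week 16:

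- Placebo: 0.783/40 = 0.01958
- Low: 0.01958 − 0.049/20 = 0.0171
- Medium-low: 0.01958 + 0.049/20 = 0.0220
- Medium-high: 0.01958 + 0.196/20 = 0.0294
- High: 0.01958 + 0.587/40 = 0.0343

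The ratio is 7 : 9 : 12 : 14. A Low patient who received the High regimen throughout would have twice the planned dose of the arm under which he or she is reported.

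**4. Tracing a reassigned Arm 5 patient through the displays**

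| Display | Set | Column | Data after Week 16 |
|---|---|---|---|
| AE and laboratory abnormalities before the first maintenance dose at or after Week 16 | SAF | Arm 4 | none |
| AE and laboratory abnormalities after that dose | SAF-post 16 | Arm 5, and Arm 1+3+5 pool | correct regimen |
| Whole-period AE tables | SAF | Arm 4 | counted under Arm 4 |
| Final laboratory last/min/max | SAF | Arm 4 | counted under Arm 4 |
| Final vital-sign last/min/max | SAF | Arm 4 | counted under Arm 4 |

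In the last three rows, 52 − 16 = 36 of the 52 planned treatment weeks are spent on another regimen.

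**5. Effect on an Arm 4 rate.** Let r of 20 Arm 4 patients have the event, and add one patient.

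- With the event: (r + 1)/21 − r/20 = (20 − r)/420.
- Without it: r/21 − r/20 = −r/420.
- The largest shift in either direction is 20/420 = 1/21 = 4.8 points.
- At r = 12 it is 8/420 = +1.9 or −12/420 = −2.9 points.

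For the carry-over alone, the patient is already in the 21. An event that occurs only after Week 16 adds 1/21 = 4.8 points; otherwise nothing changes.

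**The case against.** The strongest reply is that the misallocation text sits in the same section as the set definitions and can be read as the working meaning of actual treatment. Its reason is confined to small errors. Gross misdosing is also unlikely, because the IRT assigns individually numbered syringes at each visit. A grossly misdosed patient would be visible: incorrect dosing is coded (C2.01, C2.02) and listed per patient, and the amount received is summarised. This lowers the expected impact. It does not remove the conflict, because neither definition refers to the rule and the rule itself carries no limit.

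On the carry-over, SAP 7.8, 7.8.2 and 7.8.3 do not say how a reassigned patient is treated, and SAP 6.1 leaves technical details of the regrouped analyses to an ADS Plan that is not available here. That plan may settle the matter, but the SAP text does not.

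A reader might infer more than the documents support:

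- *That the patient sits in Arm 4 for the whole trial.* The move is written for the SAF only. The separate post-Week-16 tables use SAF-post 16, which keeps the patient in Arm 5.
- *That being in two arms in one report is itself an error.* Assignment by period is what the SAF-post 16 definition calls for. The fault lies in displays that carry one label across both periods.
- *That each added patient moves Arm 4 by 5 points.* The denominator becomes 21, so the ceiling is 4.8 points and the usual shift is smaller.

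**Conclusion.** The point stands in two limited parts. The as-randomised rule conflicts with the definitions of both safety sets, and it reaches further than its own reason. The Arm 4 label for a drug-exposed Arm 5 patient has no end date, so in SAF displays that span Week 16, followed as written, data on the Arm 1/3/5 regimen are counted under Arm 4. The post-Week-16 AE and laboratory-abnormality tables are not affected.

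The size is modest: at most 4.8 points on an Arm 4 rate per reassigned patient, at planned arm sizes. It arises only if misdosing occurs, and the documents give no expected frequency. Safety analyses are descriptive with no hypothesis testing, so type I error and power are unchanged. The twofold dose gap between Low and High describes an extreme case of regimen-long misdosing, not an expected one.

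It is still worth correcting in advance. SAP Table 6.2: 1 says incorrect dosing can be finally judged only after database lock with unblinding information, so the classification should leave no room for choice by then.

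**What to change.** In SAP 6.3:

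1. **End the Arm 4 label** at the first dose at or after Week 16. A patient randomised to Arm 5 then contributes no later data to the Arm 4 column of the whole-period AE, laboratory or vital-sign displays. Keep the existing rule that moves a drug-exposed Arm 5 patient out of placebo before Week 16.
2. **Limit the as-randomised rule** for Arms 1-4 (SAF) and Arms 1-5 (SAF-post 16) to the minor errors its reason describes, with the boundary stated before unblinding. Report a patient who received another arm's regimen throughout the period under the regimen actually received. Because Arms 1, 3 and 5 share a regimen after Week 16, say which column such a patient enters; the pooled Arm 1+3+5 group is the natural place.
3. **List the departure** in SAP Section 4 for whatever as-randomised reporting remains.

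Assigning by nearest total dose is not a good substitute. It could return a placebo patient with a few active syringes to placebo, move Arm 1-4 patients for errors of a few syringes, and tie between Arms 1, 3 and 5 after Week 16.

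The cost is a few sentences and one derived variable from medication numbers already recorded in the eCRF. A few patients may stand under different arms in the efficacy and safety tables, which the set definitions already imply.

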6.5 POOLING OF CENTRES

There is no plan to perform statistical analysis by pooling centers.

6.6 HANDLING OF MISSING DATA AND OUTLIERS

Section 7.5 of the CTP describes the handling of missing data.

The original results (OR) approach implies the presentation of data exactly as observed (not using time windows).

OR analysis will be performed on parameters and endpoints that are either not affected by patients' rescue therapy use (e.g. plasma concentration level of Spesolimab, rescue therapy use itself), or, if it is not meaningful to apply any imputation rule for the replacement of missing values

6.6.1 Withdrawals

The reasons for withdrawal from treatment will be reported as indicated on the eCRF.

6.6.2 Efficacy data

Based on the different reasons for patients' data missing for different endpoints, various approaches will be used to assess the impact of missing data on the efficacy endpoints of this trial, depending upon the type of the endpoint (cf. [Table 6.3: 1](#)). Approaches to be applied are described below.

Missing data imputations of PPP Pain VAS, PPP PGA and PPP ASI related endpoints at the primary analysis of the trial may be performed using all data up to the first maintenance dose at or after week 16 if available. Missing data imputations of other endpoints at the primary analysis will be performed using all data up week 16.

Continuous efficacy endpoints

For efficacy endpoints which are continuous in nature, the use of a restricted maximum likelihood (REML)-based mixed model repeated measures (MMRM) approach as the primary method, if applicable, will ensure that missing data are handled implicitly, via a missing at random (MAR) assumption, by the statistical model.

In order to check the robustness of MMRM method to missing data, a sensitivity analysis will be performed using Multiple imputation with jump to reference method (only for primary analysis at week 16):

As the first step, the non-monotone missing data of PPP ASI total score will be imputed using Markov Chain Monte Carlo (MCMC) simulation and standard techniques. 100 imputations will be performed to ensure adequate efficiency and stability of the estimation for missing data. In a second step, for each imputation, the monotone missing data of patients that were still ongoing in the trial will be imputed once by standard sequential linear regression MI including treatment as categorical covariate and PPP ASI from baseline up to week 16 as

continuous covariates (other missing values will also be imputed as a by-product but subsequently deleted).

In a third step, the monotone missing data of patients who early discontinued study treatment before week 16 will be imputed using a residual-based jump to reference method. The implicit assumption underlying this step is that patients in the active treatment groups are assumed to lose any treatment effect if they early discontinued from the trial treatment. Covariate-adjusted differences between each treatment arm and placebo (i.e. 0 for those in the placebo arm) will be calculated for each visit of each imputed data set using ANCOVA (with treatment as categorical covariate and baseline PPP ASI as continuous covariates). The relevant treatment effects are then deducted from the measurements in each data set, i.e. the expected effects of treatment are removed. Sequential linear MI is then performed once per modified imputed data set, but only including patients in the placebo arm and those that require imputation at the visit being imputed, i.e. imputation will be solely based on the placebo distribution. The imputation model will include PPP ASI values at previous time points (including baseline) as covariates. After this imputation, all originally-observed values will be restored. All monotone missing data will therefore follow the distribution of the placebo arm, jumping from one arm's distribution to the placebo's at the point of start of the missingness, while still accounting for the past within-treatment performance (the residuals).

For each imputed complete dataset, an ANCOVA (Analysis of Covariance) model for Week 16 data analogous to the primary MMRM model will be used for the analysis. The results will be pooled using Rubin's rules across the 100 imputations and the primary MCPMod analysis will be repeated on the summarized outcomes.

The following additional methods will be used to display the continuous data:

- Observed cases (OC) approach will include all collected data, with no imputation performed on the missing data. Such an OC approach will exclude all values measured after intake of a rescue therapy or after 6 weeks following last drug administration if a patient discontinued treatment early.
- Observed cases including all observed data (OC-IR) will be used as a sensitivity method for data display and is an extension of the OC approach which includes additionally all values which were measured after rescue therapy or treatment discontinuation.

Binary efficacy endpoints

For all binary endpoints (i.e. endpoints that are either 1 (patient responded) or 0 (patient did not respond)), the following will be performed as the primary imputation approach (analysis type: No Response Imputation [NRI]):

- If there are data at visits both before and after the visit with a missing outcome, then impute as success only if both neighbouring visits also represent a success (independent of whether the preceding and following observations were selected for analysis based on time windows described in [Section 6.7](#) and no rescue treatment has been given during this period);
- Otherwise, impute as a failure to achieve a response

Other imputation scheme will be also considered for analysis of the secondary binary efficacy endpoints.

- Best response imputation (BRI): impute all missing values based on the best response observed for the patient at visits prior to withdrawal/occurrence of missing data (independent of whether the observations were selected for analysis based on time windows described in [Section 6.7](#)). If there is no non-missing data available (including baseline), then the missing value will be imputed as a failure.

OC and OC-IR methods will be also used to display the binary data.

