3. DESCRIPTION OF DESIGN AND TRIAL POPULATION

3.1 OVERALL TRIAL DESIGN AND PLAN

This is a randomised, double-blind, placebo-controlled, parallel-design dose-finding trial comprising of 4 active doses compared to placebo. Active treatment arms consist of active loading dose and active maintenance treatment. Two different loading doses and two different maintenance treatment doses are to be tested up to Week 16 (to give four different BI 655130 dose regimens). From Week 16 onwards, three different maintenance treatment doses are to be tested. The trial design is illustrated in [Figure 3.1: 1](#).

Approximately 140 eligible patients with Palmoplantar Pustulosis will be randomised in a 2:1:1:1:2 ratio to one of the 5 following treatment arms:

Arm 1: BI 655130	 (N=40)
Arm 2: BI 655130	 (N=20)
Arm 3: BI 655130	 (N=20)
Arm 4: BI 655130	 (N=20)
Arm 5: Placebo	 (N=40)

The randomisation will be stratified for Japan versus non-Japan and will be done to assure that sufficient patients per treatment arm are recruited specifically within each region (Japan vs non-Japan). Screening of patients into any single region (Japan or non-Japan) will be closed in order to ensure that not more than 91 patients are randomised into that region. The rationale is to allow for a thorough assessment in the Japanese population and to assess whether there is a difference in treatment effect between Japanese vs non-Japanese patients (which is hypothesized based on clinical trials in Japan which tend to show larger treatment effects in PPP patients than have been observed in European clinical trials). This stratum will be included into the analyses of the primary endpoint.

 This is required to keep the blinding. Please refer to [Sections 4.1.1](#) and [4.1.5.1](#) for details.

An overview of all relevant trial activities is provided in the [Flow Chart](#). For visit schedules and details of trial procedures at selected visits, refer to [Sections 6.1](#) and [6.2](#), respectively.

The patients are followed-up until Week 68 which is 16 weeks after the last dose of the study drug at week 52 (Residual Effect Period of 16 weeks).

[figure not shown]

Figure 3.1: 1 Trial design

An independent Data Monitoring Committee will evaluate safety and efficacy data on a continuous basis. For details please refer to [Section 8.7](#).

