7.4 PRIMARY ENDPOINT

For the primary endpoint analysis, first a mixed effect model for repeated measurements (MMRM) is calculated to estimate the treatment effects and the corresponding covariance matrix. Using the MCPMod approach ([11](#), [12](#)), these estimates are then further used to (1) test for a non-flat dose response curve and (2) to identify suitable dose-response shapes out of a selection of candidate models. The final model will then be calculated by averaging over all significant model shapes.

Details on both the specification of the MMRM and the MCPMod approach are given in the CTP Section 7.2.2. Sample size calculations are described in CTP Section 7.5.

The primary analysis of primary endpoint will be based on the FAS. Any data collected after use of any rescue therapy or after 6 weeks following last drug administration if a patient

discontinued treatment early will be censored as the primary estimand (EC).

MMRM analysis

The % change in PPP ASI from baseline (Visit 2), at Visits 3, 4, 5, 6, 7, 8 and 9 (Weeks 1, 2, 3, 4, 8, 12 and 16) will be evaluated using an MMRM accounting for the following sources of variation: 'baseline' as a continuous covariate, and 'visit', 'treatment', 'region' (stratification according to Japan vs. non-Japan), 'visit*treatment' and 'visit*baseline' interaction as fixed effects as well as the random 'subject' effect. The unstructured covariance structure will be used to model the within patient measurements. To estimate denominator degrees of freedom the Kenward-Roger approximation will be used.

In the event of model non-convergence, the methods described in [Section 9.3](#) will be utilized to resolve this.

SAS code for MMRM:

The following SAS code will be used to calculate the MMRM.

```
PROC MIXED DATA=alldat cl method=reml;
  CLASS visit trt stratum subject;
  MODEL ept = stratum visit*trt base*visit / ddfm=kr s CL;
  REPEATED visit / subject= subject type=un r rcorr;
  LSMEANS visit*trt / pdiff=all om cl alpha=0.05 slice=visit;
RUN;
```

Results of the MMRM (N, mean, SE and 95% CI per dose group and timepoint) will be presented in tables and displayed graphically.

MCPMod Analysis

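### The jump-to-reference sensitivity analysis imputes without region, although region is the stratification factor and is in the analysis model applied afterwards

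*SAP*

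**What the plan says.** Protocol 3.1 states: "The randomisation will be stratified for Japan versus non-Japan", and adds: "This stratum will be included into the analyses of the primary endpoint". Protocol 7.4 names no other stratification factor. In the MMRM code of SAP 7.4, region enters as stratum: "MODEL ept = stratum visit*trt base*visit / ddfm=kr s CL".

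SAP 6.6.2 builds the EC-MI analysis in three steps.

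- **Step 1** fills intermittent gaps in the PPP ASI score by MCMC. No covariates are listed.
- **Step 2** imputes monotone gaps in patients still ongoing, under missing at random. It uses "standard sequential linear regression MI including treatment as categorical covariate" together with the PPP ASI scores.
- **Step 3** is the jump to reference and covers patients who stopped treatment before Week 16. Arm differences at each visit are estimated "using ANCOVA (with treatment as categorical covariate and baseline PPP ASI as continuous covariates" and removed. The missing scores are then drawn from a regression based on the placebo arm: "The imputation model will include PPP ASI values at previous time points (including baseline) as covariates". Observed values are restored afterwards.

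Each completed data set is analysed by a Week 16 ANCOVA that mirrors the primary MMRM. The results are pooled by Rubin's rules and MCPMod is repeated. Protocol 7.3 names no imputation covariates and leaves the details to the SAP.

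**The concern.** The covariate lists in steps 2 and 3 are explicit and region is on none of them, while the model fitted to the completed data contains region. The imputation model is thus poorer than the analysis model in a factor that the sponsor chose to stratify on.

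Two things follow. A patient who stopped before Week 16 is imputed from a placebo distribution pooled over Japan and non-Japan, conditional on that patient's own baseline and earlier scores. An ongoing patient with monotone gaps is imputed under missing at random, also without region. If the Week 16 course differs by region beyond what the earlier scores already show, imputed values are pulled toward the other region. The arm contrasts can then shift when stopping is related to region and uneven between arms.

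The analysis exists to test how far the MMRM result depends on its missing-data assumption. If EC-MI and the MMRM disagree, part of the gap could come from the missing covariate and not from the assumption under test.

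**Working it through.** **1. Which models contain region**

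| Model | Terms stated | Region? |
|---|---|---|
| Primary MMRM (SAP 7.4) | region, visit by treatment, visit by baseline | yes |
| Week 16 ANCOVA after imputation (SAP 6.6.2) | mirrors the MMRM | yes |
| Step 2 regression | treatment, PPP ASI scores | no |
| Step 3 ANCOVA for arm differences | treatment, baseline | no |
| Step 3 placebo-based regression | earlier scores including baseline | no |

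**2. Design inputs.** Protocol 7.5 gives 140 patients (40/20/20/20/40), a placebo mean of -25%, a maximum difference of 30 points and an SD of 35 before truncation at -100%. As a check on these inputs, 10,000 trials per scenario were simulated with the contrasts of SAP Table 7.4: 2, a one-sided 5% test and AIC-weighted averaging (weights proportional to exp(-0.5 AIC)). Relative dose spacing was inferred from the linear contrast. For the linear 30-point scenario this gave 92.2% at delta 20 (protocol 93.2%) and 75.3% at delta 25 (protocol 77.1%). The exponential scenario at delta 25 came out lower (75.3% against 79.0%). Rounded contrasts and simplified fitting probably explain that, and I do not read it as an error.

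**3. Effect of leaving region out.** Trials of 140 were simulated with step 3 as the SAP describes it, simplified to Weeks 4, 8, 12 and 16 and to six imputations in place of 100. Imputation was run without and with region, followed by the Week 16 ANCOVA with treatment, baseline and region. There were 300 trials per scenario and the two regions were of equal size. Stopping rate, regional difference at Week 16 and visit correlation are assumptions. Entries are the high-dose-minus-placebo estimate without region minus the estimate with region, in points.

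| Stopping | Regional difference | Correlation | Stopping unrelated to region | All active-arm stoppers from one region |
|---|---|---|---|---|
| 10% | 10 | 0.8 | +0.14 | -0.29 |
| 10% | 20 | 0.8 | -0.01 | -0.60 |
| 20% | 10 | 0.8 | +0.03 | -0.75 |
| 20% | 20 | 0.8 | +0.09 | -1.19 |
| 10% | 10 | 0.5 | +0.14 | -0.38 |
| 10% | 20 | 0.5 | -0.03 | -0.90 |
| 20% | 10 | 0.5 | -0.05 | -0.80 |
| 20% | 20 | 0.5 | +0.08 | -1.67 |

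The Monte Carlo standard error of an entry is 0.08 to 0.19. The standard error of the treatment estimate is 8.2 to 9.6 with or without region, so the largest shift is 1.67 / 9.42 = 0.18 of a standard error. In the last column the benefit looks larger without region; the sign reverses if the stoppers come from the other region. The region coefficient shrinks by about 0.4 to 3 points (for example 15.89 against 19.11). Smaller runs with a 35% region gave similar results.

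**4. Arithmetic check.** If a fraction d of an arm stops, all from a region with share p, and the regional difference is D, then the shift before any of D is carried by earlier scores is d x (1 - p) x D. With p = 0.5, d = 0.2 and D = 20 this is 0.2 x 0.5 x 20 = 2.0; the simulation gave 1.19 to 1.67. With d = 0.1 and D = 10 it is 0.5; the simulation gave 0.29 to 0.38. The patient's own scores therefore absorb part of the difference, but not all.

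**5. Feasibility.** Protocol 3.1 ensures that "not more than 91 patients are randomised into that region". The smaller region then has at least 140 - 91 = 49 patients (35%), with about 49 x 2/7 = 14 on placebo.

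**The case against.** The strongest reply is that the omission is harmless parsimony. Step 3 is fitted on about 40 placebo patients and already conditions on several earlier scores. Protocol 7.2.2 itself treats region as the first term to drop if the MMRM does not converge. Reference-based imputation departs from the analysis model by design. No inference on the region coefficient from this analysis is planned in the visible text, so its shrinkage has no direct consequence. All of this stands as an argument about size. It does not explain why a stratification factor that the analysis model retains should be absent, and a main effect is feasible with about 14 placebo patients in the smaller region.

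A reader might also infer more than the documents support:

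- **That every patient with missing data is imputed from pooled placebo.** Jump to reference applies only to those who stopped treatment before Week 16. Ongoing patients are imputed with their own arm in the model, and step 3 keeps each patient's baseline, earlier scores and residuals.
- **That the protocol expects the placebo course to differ by region.** Its rationale cites "clinical trials in Japan which tend to show larger treatment effects in PPP patients than have been observed in European clinical trials". That concerns treatment effects. A region main effect would not capture a treatment-by-region difference, and the MMRM has no such interaction either.
- **That this is the only sensitivity analysis.** SAP Table 6.3: 1 lists several others for the primary endpoint, among them EC-ID, which keeps data after treatment discontinuation. EC-MI is, in the visible text, the only one that imputes under an assumption other than missing at random.

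**Conclusion.** The omission is confirmed on the stated text: region is absent from the step 2 regression and from both step 3 models, and present in the ANCOVA that follows. Imputation code in sections not available here might differ, but the visible covariate lists are explicit.

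The consequence is minor. The shift is about 0 when stopping is unrelated to region, and about 0.3 to 1.7 points when all active-arm stoppers come from one region, on a standard error of about 8 to 10. These figures assume 10 to 20% stopping, a 10 to 20 point regional difference, visit correlation of 0.5 to 0.8 and equal regions; none of these values is in the documents. Step 2 was not quantified separately. The primary MMRM is untouched, and nothing here suggests that a trial conclusion would change. This is a free improvement of low priority: it lets a difference between EC-MI and the MMRM be read as the effect of the missing-data assumption.

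**What to change.** In SAP 6.6.2, add region (Japan vs non-Japan) as a main effect to:

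- the step 2 sequential regression;
- the step 3 ANCOVA that estimates arm differences;
- the step 3 placebo-based regression.

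In the same edit, state whether the step 1 MCMC is run by treatment arm or region, since no covariates are listed there. The cost is one already collected covariate in each of three models, with no new data and no change to the primary analysis.
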